Side effects of two different mandibular advancement devices (MAD) in the treatment of snoring and obstructive sleep apnea syndrome (OSAS)

Side effects of mandibular advancement devices

Unique Protocol ID: 001072019

Document Date: April 4, 2019

Abstract

Sleep-related breathing disorders (SBAS) are one of the most common causes of non-restorative sleep.

Sleep therapy options include positive pressure ventilation with continuous positive airway pressure (CPAP) masks, mandibular advancement of the mandible with mandibular advancement devices (MAD), back restraining, weight reduction, ear, nose and throat surgical procedures, bimaxillary or mandibular remodeling osteotomies, and neurostimulation procedures N. hypoglossal. In mild to moderate obstructive sleep apnea syndrome (OSAS), MAD, back suppression and weight reduction are potential treatment options. This study aims to identify possible side effects in the temporomandibular system that occur during nocturnal support of a mandibular arch over two years. Two different MADs are compared in terms of construction, height (bite elevation) and protrusion mechanics: the H-MAD with an autumn hinge and the SomnoDent Fusion™ (called F-MAD) with sliding side wings. In addition, it is to be evaluated whether hinge system according to Herbst as a protrusion-controlling element and the reduction of the splint body for a reduced bite elevation leads to a significant reduction of side effects compared to the F-UPS.

Detailed description

Sleep-related breathing disorders (SBAS), particularly obstructive sleep apnea syndrome (OSAS), are one of the most common causes of non-restorative sleep. Disturbances of sleep disorders include apneas and hypopneas associated with either or not pharyngeal obstruction and hypoventilation. Depending on the type of respiratory disorder present, they are associated with hypoxemia and may cause hypercapnia or acidosis.

The consequences of obstructive narrowing of the pharynx are far-reaching. Studies have shown that patients with OSAS have comorbidities such as neurological complaints, heart attacks, dementia, cardiovascular complaints, myocardial infarction, and a higher mortality rate.

Sleep fragmentation caused by respiratory disorders during sleep and wakefulness reactions (arousals) can lead to daytime sleepiness and concentration disorders. In the longer term untreated arousals and apneas are associated with an increased risk for arterial hypertension, stroke, myocardial infarction, diabetes mellitus and libido loss.

OSAS management includes positive pressure ventilation with continuous positive airway pressure (CPAP) masks, mandibular advancement of the mandible with mandibular advancement devices (MAD), weight loss, ear, nose and throat surgical procedures, bimaxillary or mandibular remodeling osteotomies, and neurostimulation procedures of the hypoglossal nerve.

Several studies have shown that the use of MADs is inferior in reducing the severity of OSAS in comparison to CPAP therapy, but its efficacy is comparable and preferred by patients in mild to moderate OSAS.

Due to the forward displacement of the lower jaw for several hours at night, similar symptoms as in temporomandibular dysfunction (TMD) patients may occur. The symptoms may be pain or stiffness on the masticatory muscles or temporomandibular joints.

This study aims to identify possible side effects in the temporomandibular system that occur during the course of two years of nocturnal MAD delivery. Two different

appliance systems are compared in terms of construction height (bite elevation) and protrusion mechanics: the H-MAD™ with a hinge system according to Herbst and the SomnoDent Fusion™ (called F-MAD) with sliding side wings.

Hypotheses

1. F-MAD significantly increases pain in the craniofacial area (primary target variable) compared to H-MAD.
2. The F-MAD leads to a significantly increased number of pressure-pain areas of the masticatory muscles and temporomandibular joints compared to the H-MAD.
3. The F-MAD has a higher loss of posterior contact points than the H-MAD.

Study design

Multicenter, randomized two-arm Phase IV study with active control group, stratified by gender, unblinded with respect to the examiner, blinded to the patient and statisticians in the evaluation.

Primary outcome variable

The primary outcome variable is defined as the change of orofacial pain after applying the MAD as measured by numeric rating scale (NRS; 0-10, 0: no pain, 10: worst imaginable pain) at the time of the follow-up appointments.

Secondary outcome variables:

Dental variables:

- Number of pressure pain points on palpation of the masticatory muscles and in the area of the temporomandibular joints
- Number of posterior contact points
- Clinical occlusion protocol
- digital occlusion protocol determined with occlusal registrations in habitual intercuspidation; Evaluation by software GEDAS (Greifswald Digital Analyzing System) based on transparent contact areas.

Sleep-related variables:

- Sleep quality (Pittsburgh Sleep Quality Index PSQI)
- Epworth Sleepiness Scale (ESS)
- STOP-Bang questionnaire
- Oral Health Impact profile (OHIP-5)
- Apnea Hypopnea Index (AHI)
- Desaturation index (DI)
- Average oxygen saturation during sleep

Methods of data collection

The data collection is paper-based. For each patient, an analog study file is created. The main contents of the study file are the case report forms (CRF) and the questionnaires (PSQI, ESS, STOP-Bang, OHIP-5) and the AHI and EI).

The Pittsburgh Sleep Quality Index (PSQI) retrospectively asks for a four-week period the incidence of sleep disturbing events, sleep quality assessment, sleep habits, sleep latency and sleep duration, sleeping medication use, and daytime sleepiness. A total of 18 items are used for quantitative evaluation and assigned to 7 components, each of which can assume a value range of 0 to 3. The total score is the sum of the component scores and can vary from 0 to 21, with a higher score corresponding to a reduced sleep quality. There is an empirically determined cut-off value (of 5), which allows a classification into "good" and "bad" sleepers.

The Epworth Sleepiness Scale (ESS) is a short questionnaire for the detection of daytime sleepiness, in which the probability of falling asleep or falling asleep in eight typical everyday situations is retrospectively inquired. It can generally be used for sleep disorders, especially for hypersomnia, as a screening instrument for the global detection of daytime sleepiness or as an indication of the presence of hypersomnia. In addition, it is also suitable for measuring progress or success (for example in CPAP patients).

The STOP-BANG questionnaire is a screening for the presence of OSAS in the general population. A low OSAS risk exists if 0-2 answers yes, a medium OSAS risk if yes to 3-4, and high OSAS risk if yes to 5-8 questions.

The Oral Health Impact Profile (OHIP) is a measurement tool for assessing the oral health-related quality of life in adults. It can describe the individual oral health status of patients and measure and compare disease-related burdens in the course.

The Graded Chronic Pain Scale (GCPS) questionnaire records pain intensity and the presence of functional or dysfunctional chronic pain.

The Apnea Hypopnea Index (AHI) is a measure of how many breathing pauses in the form of apneas and hypopneas a patient experiences while sleeping. The AHI is determined in the sleep laboratory via a polysomnographic recording. Depending on the value of AHI, a distinction is made between mild, moderate and severe sleep apnea.

The desaturation index (DI) is the number of oxygen desaturations per hour of sleep. The questionnaires (PSQI, ESS, OHIP-5, STOP-BANG, GCPS) are completed by the investigators in the form of an interview with the patient. AHI and DI are collected in the sleep laboratory.

Occlusion protocol: The tooth contacts between upper and lower jaw are recorded once with thin (ShimStock) slides for each tooth during the clinical examination. Furthermore, bite registrations in habitual intercuspidation (centric occlusion) are created from thinly flowing, addition-crosslinked silicone and scanned with a document scanner for evaluation in transmitted light. Layer thicknesses $\leq 20 \mu\text{m}$ are interpreted as occlusal contacts and assigned to the anatomical structures of the chewing surfaces (Greifswald Digital Analyzing System).

Functional Examination is designed to record masticatory jaw joint disorders based on a detailed history and subsequent clinical examination, palpation and orofacial inspection. For this purpose, a current and standardized examination procedure, the Diagnostic Criteria for TMD (DC/TMD) is used. This research toolkit also includes the Questionnaire on Chronic Pain Grading (GCPS), Jaw Functional Limitation Scale (Jaw Functionality), and Oral Behavior Checklist.

Treatment group 1:

Patients with snoring and OSAS, Therapy SomnoDent Fusion™ Fusion MAD with sliding side wings (F-MAD).

Picking up to reach a 5 mm incisor distance using George Gauge with a lower jaw advancement of 5 mm with insertion of the MAD up to a final titrated mandibular advancement in the therapy phase.

Treatment group 2:

Patients with snoring and OSAS. Therapy with MAD type H-MAD with lateral hinges according to Herbst.

Bite elevation until reaching a min. 2 mm interocclusal distance and the lowest possible incisor distance with a lower jaw advancement of 5 mm with insertion of the MAD up to a final titrated mandibular advancement in the therapy phase.

Group strength: 97 patients per group (194 patients in total)

Description of the recruitment:

Patients are recruited at 7 dental or oral surgery clinics that specialize in the treatment of OSAS patients through MAD and are networked with referring sleep medicine centers.

Inclusion criteria:

- Patients with medical indication for mandibular protrusion (MAD) due to OSAS
- Therapy request for primary ronchopathy
- Age \geq 18 years and \leq 75 years
- BMI \leq 35
- Mandible protrusion of min. 5 mm possible (titration starts at 5 mm)
- At least 8 teeth or 4 implants per jaw
- Fixed dentures and stable, removable partial denture
- at least support up to the area of the 2nd premolars on both sides
- Business ability and the existence of the signed declaration of consent

Exclusion criteria:

- Polyarthritis
- Fibromyalgia, neuralgia
- Central sleep apnea syndrome
- untreated generalized periodontitis PSI > 2
- Chronic dysfunctional pain after GCPS grade 3-4
- Age: <18 years or > 75 years
- long-term use of psychotropic and analgesics (> 4 weeks)
- pregnancy
- Participation in another interventional clinical study (currently up to three months before inclusion)

Experimental procedure

Calibrating the examiner

All Dentists will be trained and calibrated by the study leader prior to the start of the study in the investigation tools and the data collection. Training Center is the practice of Dr. med. med. Dr. med. dent. [name], [name]. At a still to be determined weekend, all the doctors are instructed in the course of the investigation and the questionnaire survey explained. Furthermore, the clinical functional examination will be demonstrated and subsequently practiced by the study physicians. All the doctors are calibrated to the palpation pressures to be applied and the overruling determined in a final test.

Sleep Laboratory

All patients received a structured general and somnological anamnesis and examination (height, weight, BMI, ESS, STOP-BANG, PSQI) in a first visit to the sleep laboratory. In addition, a stationary polysomnography or an outpatient polygraphy was performed there. Patients were referred to specialist dental practices for the preparation and integration of a MAD based on the diagnosis of sleep medicine for treatment of sleep apnea syndrome or snoring.

Baseline examination

Patient history and the dental status and periodontal screening index (PSI) are used to check inclusion and exclusion criteria for splint therapy. Subsequently, a functional status, occlusion protocol clinical and digital (GEDAS, Greifswald Digital Analyzing System), the questionnaires for pain chronification (GCSP) and quality of life (oral health impact profile, OHIP-5) are included.

To assess the health of the teeth and to ensure the success of treatment, an X-ray survey (panoramic radiograph) must be available before the treatment, which is not older than 6 months. Such an X-ray photograph can be made by the dentist or the specialized dental practice.

The functional status is determined by means of a standardized functional finding (DC / TMD). The questionnaires are based on validated recommendations. All examination procedures are part of the routine patient diagnostics, which have been standardized for the individual practices for this project.

Randomization

The randomized grouping into blocks at a ratio of 1: 1 takes place over sealed envelopes containing the allocation key for the respective MAD. The assignment is stratified according to gender because gender is a strong predictor of sleep disorders and also temporomandibular dysfunctions.

Impression taking

Subsequently, the upper and lower jaws are molded to make the respective therapeutic splints and the protrusion registrations are taken. The starting position of the mandibular protrusion is set to 5 mm by default.

Integration of the MAD (start of treatment)

The laboratory-made MAD (F-MAD / H-MAD) is integrated (with a mandibular protrusion of 5 mm) and checked for a comfortable fit. Here, we paid attention to a

surface contact between OK-UK splint, and a tension-free fit of the splint portions on the rows of teeth. If necessary, interfering contacts are ground in. The patient is instructed to always wear the splint during sleep.

All patients receive an extended guide to jaw gymnastics with the instruction to do it in the morning after waking up and in the evening before falling asleep.

First control appointment (4 weeks after incorporation)

Four weeks after incorporation, the titration phase begins, d. H. the slow adjustment of mandibular advancement to optimize sleep medical parameters while minimizing unwanted side effects. The feed rate should be adjusted until clinical and sleep medical parameters are optimal or the patient can no longer tolerate further advancement.

The functional findings, the occlusion protocol, the questionnaires ESS, OHIP-5 and PSQI are collected.

Second control appointment (6 months after start of therapy)

Six months after the start of treatment, another examination is carried out in which the functional findings, the occlusion protocol and the questionnaires ESS, OHIP-5 and PSQI are collected.

Third control appointment (12 months after start of therapy)

A third check is made 12 months after the start of therapy. The functional findings, the questionnaires ESS, OHIP-5 and PSQI, the occlusion protocol, the bite registration for scanning and contact point analysis (GEDAS, Greifswald Digital Analyzing System) are collected.

Fourth control appointment (24 months after start of therapy)

The last examination is 24 months after the start of therapy. The functional findings, the questionnaires ESS, OHIP-5 and PSQI, the occlusion protocol, the bite registration for scanning and contact point analysis (GEDAS, Greifswald Digital Analyzing System) and new models are collected.

Sample size estimation

Determine the required sample size based on the numerical pain scale 0-10 for the primary target variable. Norms are pain scores of 3-5 (myofascial pain) in patients with temporomandibular dysfunction (TMD). To determine a mean difference of 1 level (standard deviation of 2) (1, 2) between the MAD, they must each comprise 78 patients.

Test method:

Wilcoxon-Mann-Whitney test with a two-sided $\alpha = 0.05$, a power = 0.90 assuming the family of logistic distributions (G * Power, version 3.1.)

The net sample consists of 156 persons. The annual dropout is 10% (3), so that for a study period of 2 years a total sample of 194 persons must be calculated (194 - 20 = 174 after 1 year, 174 - 18 = 156 after 2 years).

Statistical evaluation

The evaluation of the primary (and also the secondary) target variable is carried out according to the power analysis using ordinal regression as a generalization of the Wilcoxon-Mann-Whitney test. Adjustments are made according to sex as a stratification variable, age ("restricted cubic splines" with 3 nodes, which requires 2 coefficients), the baseline value of the respective target variable, the centers, the school education and, if appropriate, the blocks of randomization.

The intention-to-treat analysis set includes all patients assigned to one of the two groMAD and the built-up track; the "per protocol" set includes all patients with supported splints, primary target size data at 24 months and no relevant deviations from the study protocol. Sensitivity analyzes are performed with replacement of missing values via multiple imputation.

An interim evaluation is not planned.

Subgroup analyzes are not planned.

The 95% confidence interval is interpreted; the list of primary and secondary target sizes listed above allows $\alpha = 0.05$ to be left uncorrected (Cook & Farewell) (4).

At the University Medicine Greifswald, Center for Dental, Oral and Maxillofacial Surgery (ZZMK) the blinded evaluation of the data takes place.

This study is conducted with particular attention to the contents of the following laws and guidelines:

- Declaration of Helsinki in its current version (Fortaleza, 2013)
- Medical Devices Act - MPG
- Medical Device Operator Ordinance - MPBetreibV
- State Data Protection Act - DSG M-V
- General Data Protection Regulation - EU GDPR

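### The plan does not settle whether the ordinal response is the change in NRS pain or the follow-up NRS score; if it is the change and most patients are pain-free, the device odds ratio is attenuated and some power is lost

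*Combined protocol and SAP*

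**What the plan says.** All places are in the combined protocol and SAP.

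- **Primary outcome variable:** "The primary outcome variable is defined as the change of orofacial pain after applying the MAD as measured by numeric rating scale", on an 11-point scale ("NRS; 0-10, 0: no pain, 10: worst imaginable pain"), measured "at the time of the follow-up appointments". No single visit is named.
- **Statistical evaluation:** primary and secondary target variables are analysed "using ordinal regression as a generalization of the Wilcoxon-Mann-Whitney test". The covariates include "the baseline value of the respective target variable". The per-protocol set requires primary data at 24 months.
- **Sample size estimation:** a difference of 1 level with SD 2 on the 0-10 scale, logistic distribution, two-sided alpha 0.05 and power 0.90 give 78 per arm, 156 net. The pain level used for orientation, 3 to 5, comes from patients with temporomandibular dysfunction. No SD of a change is given.
- **Inclusion and Exclusion criteria:** no minimum pain is required, and GCPS grade 3-4 is excluded.
- **Secondary outcome variables:** tender points and posterior contacts are listed as numbers, not as changes.

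The documents give no baseline pain distribution, no expected share of patients at 0 and no correlation between baseline and follow-up.

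**The concern.** In linear ANCOVA the choice between change and follow-up score would not matter: with baseline in the model, both give the same device effect. Ordinal regression lacks this property. The categories of the response are themselves different, so the two analyses can give different odds ratios, standard errors and p-values from the same data.

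The device odds ratio is the trial's main result. If the response is not fixed in advance, either analysis can be defended after the data are seen. If the response is the change, the analysis also moves off the scale on which the trial was sized.

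**Working it through.** **1. The plan's own figure.** Inputs from Sample size estimation: d = 1/2 = 0.5, two-sided alpha 0.05, power 0.90, logistic distribution. The Wilcoxon-Mann-Whitney efficiency relative to the t-test under a logistic distribution is π²/9 = 1.097. With 78 per arm the effective size is 78 × 1.097 = 85.5, and the noncentral t power is 0.902; with 77 it is 0.898. So 78 per arm reproduces. For dropout, 156/0.81 = 193, against 194 stated. The calculation concerns a difference between scores.

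**2. Effect on the ordinal scale.** One level at SD 2 under a logistic distribution is a log odds ratio of 1/(2√3/π) = 0.907, so the odds ratio is exp(0.907) = 2.48.

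**3. Why the two responses differ.** A patient with baseline b can only change by -b to 10-b.

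- Two patients who end at 0 from baselines 1 and 4 share one score category, but have changes of -1 and -4.
- A patient who starts at 0 has a change equal to the follow-up score, so nothing is lost there.
- At b = 0 a decrease has probability 0; at b = 4 it does not. A single baseline coefficient therefore cannot hold exactly at every cut-point of the change.

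**4. Size, copula model (assumed).** 156 patients, marginal odds ratio 2.48, both responses fitted with device and linear baseline. The ranges cover sets of 500 to 1,500 simulated trials per scenario.

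| Share of scores at 0 | Odds ratio, score | Odds ratio, change | Power lost with change |
|---|---|---|---|
| 50% | no material difference | no material difference | about 0 |
| 70% | 2.57 to 2.76 | 2.37 to 2.54 | about 0 to 4 points |
| 85% | 2.56 to 2.72 | 2.25 to 2.37 | about 2 to 8 points |

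At the plan's level (mean 3 or 4, SD 2; 300 trials per scenario) the two agree.

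**5. Size, second model (assumed).** The follow-up score is a rounded latent logistic value with SD 2 and a 1-point device effect, cut at 0 and 10; 2,000 trials per scenario, Monte Carlo error about 1 point. Selected scenarios:

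| At 0, baseline | At 0, follow-up | Odds ratio, score / change | Power %, score / change | Difference |
|---|---|---|---|---|
| 40% | 77% | 2.51 / 1.92 | 61.7 / 49.4 | -12.3 |
| 60% | 80% | 2.56 / 2.06 | 59.4 / 49.7 | -9.7 |
| 80% | 82% | 2.57 / 2.28 | 54.8 / 49.5 | -5.3 |
| 4% (mean 4, SD 2) | 66% | 2.51 / 2.00 | 75.0 / 66.9 | -8.1 |
| 40% | 43% | 2.53 / 2.31 | 83.0 / 80.5 | -2.5 |
| 60% | 43% | 2.54 / 2.55 | 86.8 / 86.6 | -0.2 |
| 4% (mean 4, SD 2) | 15% | 2.50 / 2.54 | 89.0 / 89.3 | +0.3 |

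The first three rows share one follow-up setting. The loss falls as more patients start at 0, which fits step 3: it comes from patients with differing positive baselines who end at 0. A zero indicator for baseline barely helps the change model (at 40% baseline and 58% follow-up zeros, odds ratio 2.05 to 2.07 and power 66.5% to 67.7%).

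**6. Type I error.** In the second model, two heavy-floor null scenarios gave 0.021 and 0.025 with change, against 0.046 with score. Null runs of the copula model gave 0.037 to 0.050. Nothing is inflated.

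**Limits.** Both models generate proportional odds on the score scale, which favours the score analysis. Centre, age and sex were left out.

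**The case against.** The strongest reply is that the plan may already mean the score. Hypothesis 1 labels craniofacial pain itself as the primary target variable, the sample size uses the 0-10 scale, and adjustment for a baseline value only makes sense for a score. The text also reads as a rough translation, so one word is thin ground for calling the model wrong. This stands in part: a reader might infer that the primary model is definitely misspecified, and the documents do not support that. But the formal definition of the primary outcome does say change, and an analyst who follows it literally would model the change.

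Second, part of the odds-ratio gap is not attenuation. In the copula model 2.48 is a marginal odds ratio, and baseline adjustment moves a non-collapsible odds ratio away from 1; the unadjusted score analysis gave 2.46 to 2.54. At 70% zeros the change model is therefore close to the simulated value. This stands. Values of 2.25 to 2.37 at 85% zeros are below 2.48 and are real shrinkage. So are the 1.92 to 2.28 in the heavy-floor rows of the second model, where 2.48 is already conditional on baseline.

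Third, the loss depends on a floor that the documents do not quantify, and it vanishes at their own planning level. This also stands. A heavy floor is plausible in snoring and sleep apnea patients with no minimum pain and GCPS grade 3-4 excluded, but it remains an assumption.

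**Conclusion.** The point holds as an unresolved definition of the primary response, with a conditional cost. If change is modelled and most patients are pain-free, the device odds ratio is attenuated and power falls by about 0 to 4 points at 70% zeros and 2 to 8 points at 85% (copula model). Under the second model the loss is about 5 to 12 points with 58 to 82% zeros at follow-up. At 50% zeros or fewer the difference is not material; the largest gap seen there was 2.5 points, at 43% zeros in the second model. At the plan's own pain level it is nil. In no scenario was change better by more than simulation error.

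Three stronger conclusions might be inferred and are not supported. The floor alone does not shrink the odds ratio, since for patients who start at 0 change and score coincide. The sample size is not shown to be wrong: 78 per arm reproduces on the plan's inputs. There is no excess of false positives. All sizes rest on assumed pain distributions.

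**What to change.** Under Primary outcome variable, define the primary variable as the NRS score at one named follow-up visit. The per-protocol definition already points to 24 months; the sponsor should confirm the visit. Under Statistical evaluation, state that this score is the ordinal response and that baseline NRS is a covariate. Report changes from baseline descriptively only.

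The secondary counts are already listed as numbers and need no rewording. The cost is two sentences, plus the decision on the visit. Data, visits, software and sample size stay the same. The change should be made before the data are unblinded for analysis.

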For each patient a study file is created, which i.a. contain the respective questionnaires, assessment of adherence, polygraphy and polysomonography measurements. The entries are with documents authentic pens, z. B. make ballpoint pen; Pencil entries are not allowed.

Corrections are made as follows: The wrong entry is crossed out with a simple line, the correct information is entered in the immediate vicinity, initialed with date and, if necessary, given with an indication of the reason for the correction. Data fields that can not be completed due to lack of information must be commented on. The test sheets are promptly filled in by persons who are entitled to the documentation, then checked by the study doctor and signed with a date.

Data Processing

The documentation sheets are checked by the monitor for completeness and plausibility (first plausibility check). Subsequently, data from independent data entry staff are entered and matched twice in the study database. During data entry, the second plausibility check is performed. Any discrepancies and implausibilities will be clarified in writing by the data submitter in writing with the study center concerned. These inquiries (queries) must be answered promptly by the study center.

Quality Assurance and Quality Control

A quality assurance tool is the calibration of the examiner. This ensures that all examiners work according to the same standards and guidelines and that there are no or negligible differences between the examiners.

The Coordinating Center Clinical Trials of the University Medicine Greifswald takes over the monitoring of the study documents and the proper and GCP-compliant study execution according to the study protocol as well as the associated data collection as part of the quality assurance.

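### Investigators complete the follow-up PSQI, ESS and OHIP-5 by interview in a trial with an unblinded examiner; self-completion before the examination would be a cheap improvement

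*Combined protocol and SAP*

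**What the plan says.** - **Mode.** Methods of data collection: "The questionnaires (PSQI, ESS, OHIP-5, STOP-BANG, GCPS) are completed by the investigators in the form of an interview with the patient". The pain NRS is not in this list.
- **Blinding.** Study design describes the trial as "unblinded with respect to the examiner, blinded to the patient and statisticians in the evaluation".
- **Follow-up schedule.** At the four-week control appointment: "The functional findings, the occlusion protocol, the questionnaires ESS, OHIP-5 and PSQI are collected". The same three questionnaires are listed at 6, 12 and 24 months. No control-visit list names the NRS.
- **Who is trained.** Calibrating the examiner addresses the dentists and says that "all the doctors are instructed in the course of the investigation and the questionnaire survey explained".
- **Who fills in forms generally.** Data collection, under Data management, has the sheets "filled in by persons who are entitled to the documentation, then checked by the study doctor and signed with a date".
- **Primary outcome.** The change in orofacial pain is defined "as measured by numeric rating scale (NRS; 0-10, 0: no pain, 10: worst imaginable pain) at the time of the follow-up appointments". Who records it, how, and whether before or after the examination are not stated.

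**The concern.** PSQI, ESS and OHIP-5 are patient-reported. In a trial that blinds the patient but not the examiner, such outcomes are protected mainly by the patient's not knowing the device. That protection weakens if someone who does know it asks the question, explains the item and writes down the answer. Arm-related prompting or recording would then enter the data at source.

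The later safeguards act too late or on something else. Blinded evaluation starts from answers already recorded. Calibration aims at agreement between examiners, not at what they know about allocation. Double entry and plausibility checks test transcription and consistency. Statistical evaluation leaves the 5% level uncorrected across primary and secondary outcomes and interprets the 95% confidence intervals, so each of the three outcomes would be read at face value.

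**Working it through.** No figure in the plan is in dispute here, so the check sets the sections side by side and counts what is exposed.

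**1. Which instruments are interviewed after randomization?** The interview sentence covers five: PSQI, ESS, OHIP-5, STOP-BANG and GCPS. The control-visit lists name three of them: ESS, OHIP-5 and PSQI. STOP-BANG is named at the sleep laboratory and GCPS at the baseline examination, both before randomization. They are therefore not counted, although STOP-Bang is a listed secondary outcome and GCPS belongs to the functional examination toolkit.

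**2. How much of the outcome list is that?** Secondary outcomes: 4 dental + 7 sleep-related = 11. Exposed: 3 of 11. Control visits: 4, so 3 × 4 = 12 interviewed forms per patient who completes follow-up. The three hypotheses concern craniofacial pain, pressure-pain areas and posterior contacts. None concerns PSQI, ESS or OHIP-5, so 0 of 3 are exposed by the interview sentence.

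**3. Is the interviewer aware of the device?** The plan says investigators conduct the interviews and that the examiner is unblinded. The training section instructs the same doctors in both the examination and the questionnaires. Methods of data collection assigns only AHI and DI to the sleep laboratory. Together these point strongly to the examining dentist. Against this, the form-completion rule admits other authorised persons. It does not, however, require them to be unaware of the device.

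**4. Can the analysis remove an influence of this kind?** Statistical evaluation analyses the outcomes "using ordinal regression as a generalization of the Wilcoxon-Mann-Whitney test", adjusted for sex, age, baseline value, centre, schooling and, if appropriate, randomization block. On the score scale, write the recorded difference between arms as δ + b, where δ is the true difference and b the difference introduced by asking and recording. Adjusting for centre removes what is common to both arms within a centre. It does not remove b, which follows the allocation. A larger sample narrows the interval around δ + b but leaves b in place.

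**5. How large is b, and in which direction?** The documents give no information on either. A rejection rate could be calculated only for an assumed b and would reflect that assumption, so none is given.

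**6. What about the primary NRS?** It is absent from the interview sentence and from the control-visit lists, and its definition gives only the scale and the occasion. Interview by the dentist, self-completion and recording by someone else are all compatible with the text.

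**The case against.** The best case for the plan is that interview is an explicit choice, the interviewers are trained on the questionnaires, the patients are blinded, and no section contradicts another. Harm needs two steps: that the interviewers know the device, and that they prompt or record differently by arm. The first is an inference in a visibly translated text with shifting role names; the second has no support in the documents. Interviews also limit blank items, which matters for the PSQI because "The total score is the sum of the component scores and can vary from 0 to 21". If the sleep-laboratory ESS and PSQI were interviewed, changing the mode later would mix mode with change over time.

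Much of this stands, and it keeps the point small. It does not remove it: training does not remove knowledge of the device, and the forms are already on paper, so the alternative is easy. A change of mode that is equal in both arms leaves the randomized comparison intact.

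Three stronger readings are tempting, and the documents do not support them:

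- **An unblinded interviewer records the primary outcome.** The plan does not say so; the mode is simply unstated.
- **The results will be tilted towards H-MAD.** The hypotheses expect more side effects with F-MAD, but no direction is stated for these three questionnaires.
- **All five interviewed instruments are affected.** STOP-BANG and GCPS are not named as questionnaires at any control visit.

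**Conclusion.** The point holds as an optional, low-cost improvement. A stated method leaves 3 of 11 secondary outcomes, at 4 control visits, open to interviewer influence of unknown size and direction, which blinded evaluation cannot remove. None of the 3 hypotheses is touched by the documented exposure. For the primary NRS, the documented gap is that recorder, mode and timing are unstated. The conclusion assumes that the investigators who interview are the examining dentists or others who know the device. If the sponsor confirms that device-unaware staff conduct the interviews, the concern about the three questionnaires largely falls away and only the NRS specification remains.

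**What to change.** **Methods of data collection**, replace the interview sentence by:

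> At the dental baseline (pain NRS, OHIP-5) and at every control visit (pain NRS, ESS, PSQI, OHIP-5) the patient completes the forms alone on paper before the examination. Patient-answered items of any STOP-BANG or GCPS taken after randomization follow the same rule. The form is checked only for blank items, which are returned to the patient without discussion of the answers; the dentist may read the form but may not alter it. The mode used for questionnaires taken before randomization, including the sleep-laboratory ESS and PSQI, is recorded.

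**Primary outcome variable**, add to the NRS definition:

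> self-completed on paper before the examination.

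**Data management**, add:

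> For patient-completed forms the study doctor signs for receipt and completeness only. The centre answers queries by checking the original form or asking the patient, with the source of any correction documented; an item that cannot be clarified is kept as recorded or treated as missing.

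**Cost.** Wording in three places and a short wait before the examination. That the practices have someone free to check for blanks is an assumption. Treatment, visits and sample size are unchanged.

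**Downsides.**
- A few more blank items are likely, which the check is meant to limit.
- Some queries may stay unresolved, since the last two visits are 24 − 12 = 12 months apart.
- The mode may differ from that of the sleep-laboratory ESS and PSQI. This would be equal in both arms, but it limits the reading of within-arm change and may slightly weaken the baseline covariate.

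**What it leaves open.** The change acts only when answers are recorded. It does not undo expectations conveyed earlier or a patient's recognition of the device, and it does not address the unblinded palpation and occlusion assessments, which bear on hypotheses 2 and 3.
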